6.1.7.3. Total Sleep Time (TST)

• Ōura Ring

For each days' worth of sleep data, the TST for the previous night will be calculated using sleep status reported between 6pm on the previous day through 9am that day. The wearable device data tracks bedtime start and bedtime end times for each of the patient's sleep epochs as well as calculates a total sleep time within that epoch. Any bedtime end that is after 6pm the night prior or bedtime start that is before 9am the day of will have that sleep epoch data row be included towards the total TST for that day. All epochs that meet criteria will have their total sleep duration (reported in seconds) summed and the TST for that day will be totaled and divided by 60 to get minutes. The 7 nights prior to Visit 1 will comprise the 7-day TST average for baseline, the 7 nights prior to Visit 2/Week 4 (V2) will comprise the 7-day TST average for V2, and the 7 nights prior to Visit 3/Week 8 will comprise the Week 8 average TST. Subjects must have >=4 nights worth of sleep data in order for the N-day average to be calculated where N is the number of non-missing TST days' worth of data to be included. See Section 13.4.1 for more details.

[figure not shown]

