Following completion of the pretreatment sleep assessment, participants will continue into an 8-week treatment period. On Day 1 of the treatment period, all eligible participants will be enrolled in the study and will begin treating their AD with ruxolitinib cream at the FDA-approved strength (1.5%) BID, applied topically as a thin film. All original areas of AD involvement identified on Day 1 (baseline), regardless of whether or not the lesion(s) improve, and any new and/or expanded areas of AD lesions will be treated until the morning of the Week 8 visit, with a total maximum allowed treatment area of ≤ 20% BSA. Sleep data from each participant will be continuously collected during the treatment period (Day 1 through Day 56 inclusive [or the day before the Week 8 visit]) with both sleep monitoring devices. Measurements of sleep at Week 8 will be compared to baseline in a pair-wise manner to determine the reduction in sleep disturbance. At the end of the treatment period (Week 8/EOT or ET), participants will discontinue treatment with ruxolitinib 1.5% cream (with the last application on the morning of this visit) and will be required to return the eDiary, Ōura Ring, and

Following completion of the treatment period (or the last application of study drug for those who discontinue early), participants will have follow-up assessments 30 (+ 7) days after the end of treatment to evaluate safety.

Throughout the study, at the times indicated in the SoA (see Table 3), participants will complete the following PROs using their eDiary: Itch NRS (daily), PROMIS Sleep Disturbance – Short Form 8b (daily), and PROMIS Sleep-Related Impairment – Short Form 8a (weekly). Additionally, the STOP portion of the STOP-BANG questionnaire will be completed during the screening visit as part of the eligibility assessment. Participants will be assessed for the safety

and tolerability of ruxolitinib cream throughout the study by monitoring the type, frequency, and severity of AEs, performing physical examinations, measuring vital signs, and conducting clinical laboratory assessments, as outlined in the SoA.

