# 5.5. Replacement of Participants

Participants meeting the following criteria may be replaced by enrolling additional participants:

- Participants who received less than 23 applications in any interval of 14 consecutive days of BID study drug administration.
- Participants with inadequate data (data missing for  $\geq 3$  days either during the pretreatment sleep assessment or between Days 49 and 56) to complete the primary analysis (eg, due to device malfunction, internet outage, unplanned travel, etc).
- Participants experiencing major changes to their sleep patterns due to a medical condition or other life situation.

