# 7. DISCONTINUATION OF STUDY TREATMENT AND PARTICIPANT WITHDRAWAL

## 7.1. Discontinuation of Study Treatment

#### 7.1.1. Reasons for Discontinuation

Participants **must** be discontinued from study treatment for the following reasons:

- The participant becomes pregnant.
- Consent is withdrawn.

Note: Consent withdrawn means that the participant has explicitly indicated that they do not want to be followed any longer; in this case, no further data, except data in the public domain, may be solicited from or collected on the participant. Participants may choose to discontinue study treatment and remain in the study to be followed for safety monitoring.

- Further participation would be injurious to the participant's health or well-being, in the investigator's medical judgment.
- Any AE of unacceptable severity as noted in Section 6.5.
- The study is terminated by the sponsor.
- The study is terminated by the local health authority, IRB, or IEC.
- Major changes to individual sleep pattern (eg, acute sickness, hospitalization, surgery, family emergency, unplanned vacation, etc) or travel plans that would interfere with sleep assessment during the study.
- Device malfunction or other reason that would interfere with sleep data collection during the 7 days prior to baseline (ie, during Day –7 to Day -1) or prior to the Week 8 visit (ie, during Day 49 to Day 56).
- The participant's AD worsens during the treatment period to an extent that, in the opinion of the investigator, it requires treatment with study drug over an area exceeding 20% BSA.

A participant **may** be discontinued from study treatment as follows:

- If, during the course of the study, a participant is found not to have met eligibility criteria, the medical monitor, in collaboration with the investigator, will determine whether the participant should be withdrawn from study treatment.
- If a participant is noncompliant with study procedures or study drug/treatment administration in the investigator's opinion, the sponsor should be consulted for instruction on handling the participant.

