## **10.4.1.** Sleep Assessment Endpoints

The following endpoints will be evaluated to determine reduction in sleep disturbance:

• TST: The total amount of time spent during a planned sleep episode

The baseline assessments of sleep will be determined as the average of the 7 days prior to Day 1. Participants with data for at least 4 days out of the 7 days prior to Day 1 will be included in the analysis. The Week 4 and Week 8 sleep assessments will be determined using the average of the sleep measurements during the 7 days prior to Week 4 (Day 21 to Day 28) and Week 8 (Day 49 to Day 56), respectively. Participants with at least 4 days of sleep measurements during Week 4 and Week 8 assessment periods will be included in the analysis. The number of days with available data will be used to calculate the average for the week. The reduction in sleep disturbance will be calculated as the difference between the sleep assessment measures between Week 8 and baseline assessments.

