## 10.4.2. Primary Analysis

The primary endpoint of the study is change from baseline in mean TST as measured by Ōura Ring wearable device at Week 8. A paired t-test will be used to test the hypothesis below for participants with both TST measurements at baseline (as determined during the pretreatment sleep assessment) and Week 8 (Day 49 to Day 56):

H0: 
$$TST_{(Week 8)} - TST_{(Baseline)} = 0$$
  
H1:  $TST_{(Week 8)} - TST_{(Baseline)} \neq 0$ 

Mean, standard deviation, 95% confidence interval of TST at each evaluable timepoint will be presented. Mean pair-wise difference and 95% confidence interval of the difference will be presented. The hypotheses above will be tested at level of significance 0.05. The primary analysis will include participants with both baseline and Week 8 TST assessments available. Missing data imputation (LOCF) may be considered as a sensitivity analysis.

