6.1.5. Analysis Visit Windows

For all analyses, early termination and unscheduled visits will be assigned analysis visits according to the analysis windows in the following table. Where multiple measurements for a particular parameter appear within an analysis window, the result closest to the target day will be used. If equidistant, the latter result will be used for the summary measure. Though all measures may not be used in the data summaries, all measurements appear in the datasets and listings.

Scheduled Visit		Analysis	Analysis	s Window
(Subject Visit	Analysis Visit	Window Target	Lower Bound	Upper Bound
Window)		Day		11
Screening	Screening	NA		
Enrollment	Day 1	1		1

(Day 1)				
Visit 2 (Week 4 ± 7 days)	Week 4	28	2	55
Visit 3 (Week 8 + 7 days)	Week 8	56	56	63
Follow-Up (30 Days Post Visit 3 + 7 days)	Follow-Up	86	64	NA

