9.5. Physical Exams

Whether physical exams were performed at visits will be listed.

10. Changes from Planned Analysis

- Inclusion of the ITT population
- Sponsor decision to cap enrollment at 47 subjects due to enrollment challenges.
- Exclusion of the Sufficiently Treated Population (STP) due to ePRO use challenges
- No formal statistical testing of the exploratory endpoints.

Statistical Analysis Plan, Sponsor: Incyte Corporation Protocol Number: INCB 18424-902 PCN Number: INCY 216559

11. **Other Planned Analysis**

No additional are prospectively planned for this study.

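### For late Week 8 visits the protocol and the SAP take the primary TST from different nights, and the SAP's epoch rule as worded excludes no epoch

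*SAP*

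**What the plan says.** **Protocol, analysis window.** Section 10.4.1 averages the sleep measurements "during the 7 days prior to Week 4 (Day 21 to Day 28) and Week 8 (Day 49 to Day 56), respectively". Section 10.4.2 repeats the days in the paired t-test: "as determined during the pretreatment sleep assessment) and Week 8 (Day 49 to Day 56". Section 5.5 uses them to define the data needed: "during the pretreatment sleep assessment or between Days 49 and 56) to complete the primary analysis". Section 7.1.1 treats the period before the visit and the fixed days as the same thing: "prior to the Week 8 visit (ie, during Day 49 to Day 56".

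**Protocol, collection and visit timing.** Section 4.1 gives two end points for sleep data collection: "Day 1 through Day 56 inclusive [or the day before the Week 8 visit". Table 3 allows the Week 8 visit up to 7 days late.

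**SAP, analysis window.** Section 6.1.7.3 states that "the 7 nights prior to Visit 3/Week 8 will comprise the Week 8 average TST", with at least 4 nights required. Section 6.1.5 lists "Visit 3 (Week 8 + 7 days" with a target of Day 56 and bounds of Days 56 and 63. Section 10 records four changes from the planned analysis, for example "Exclusion of the Sufficiently Treated Population (STP) due to ePRO use challenges". The Week 8 window is not among them.

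**SAP, epoch rule.** Section 6.1.7.3 first limits a day's TST to sleep between 6 pm the evening before and 9 am that day. It then counts an epoch if its end falls after that 6 pm *or* its start falls before that 9 am. Appendix A (Section 13.4.1) gives two further wordings. One joins the two conditions with *and*; the other asks that the epoch start or finish inside the 6 pm to 9 am interval.

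**The concern.** The primary test needs one Week 8 TST value per participant. The protocol fixes the nights by study day and the SAP fixes them by the visit date. The two agree for an on-time visit and drift apart as the visit gets later, so a participant who is fully within the visit window can have two different primary values. Under one reading of Protocol 4.1, the same participant could also be evaluable under one rule and not under the other.

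The epoch rule matters because it defines the quantity being averaged. A programmer who coded the sentence as written would add all of a participant's recorded sleep into every day.

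**Working it through.** **1. The protocol's own count.** Day 49 to Day 56 contains 7 overnight intervals, so the stated 7 days reproduces on that count. Counted as calendar days it is 56 − 49 + 1 = 8. The protocol gives no rule for dating a night. SAP 6.1.7.3 and Appendix A date it by the waking day.

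**2. Shared nights.** For a visit on day v, the SAP's nights are v−6 to v if dated by waking day, or v−7 to v−1 if dated by start day. Their intersection with Days 49 to 56 is:

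| Visit day | 56 | 57 | 58 | 59 | 60 | 61 | 62 | 63 |
|---|---|---|---|---|---|---|---|---|
| Waking-day dating | 7 | 6 | 5 | 4 | 3 | 2 | 1 | 0 |
| Start-day dating | 7 | 7 | 6 | 5 | 4 | 3 | 2 | 1 |

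Reading the protocol window as its 7 overnight intervals also gives the first row.

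**3. Evaluability.** If collection ends on Day 56 (the first alternative in Protocol 4.1), the table also gives the number of nights available to the SAP's average. It falls below 4 for visits on Days 60 to 63 (waking day) or Days 61 to 63 (start day). If collection runs to the day before the visit (the second alternative), no visit day is affected.

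**4. Size, by assumption.** The documents give neither visit-day frequencies nor nightly variability. Assume independent nights, complete data, no trend between the two windows, and a night-to-night SD s of 45 to 75 minutes. For a 7-night and an 8-night mean sharing k nights:

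SD of the difference = s × √(1/7 + 1/8 − 2k/56)

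- k = 4: 0.354s, which is 15.9 to 26.5 minutes for one participant.
- k = 0: 0.518s, which is 23.3 to 38.8 minutes.

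If every one of the 47 enrolled participants had such a visit, dividing by √47 = 6.86 gives 2.3 to 3.9 minutes (k = 4) and 3.4 to 5.7 minutes (k = 0) for the mean.

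With 7 nights in both windows the formula is s × √(2/7 − 2k/49). It gives 0.350s at k = 4 and 0.535s at k = 0, or 2.3 to 3.8 and 3.5 to 5.8 minutes for the mean, so the 7-or-8 question hardly matters here.

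**5. Epoch rule.** Under the literal *or*, an epoch is excluded from day D only if it ended by 6 pm on D−1 and also started at or after 9 am on D. It would have to end before it started, so nothing is excluded. Enumerating 55,296 possible epochs on a 15-minute grid (length up to 24 hours) confirms this:

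- *or* excludes 0;
- *and* selects 10,320;
- *and* differs from Appendix A's start-or-finish-inside wording for 630 epochs, all starting before 6 pm and ending after 9 am, hence longer than 15 hours.

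As an illustration, 7 pretreatment plus 56 treatment nights at 6.5 hours each would put 63 × 6.5 = 409.5 hours into each day.

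**The case against.** The SAP's window can be read as carrying out the protocol. The Day 49 to Day 56 label may be the nominal days for an on-time visit. Section 4.1 lets collection run to the day before the visit, and the cream is applied until the morning of the visit, so the later nights are still on treatment. On this view the silence in Section 10 is only a gap in documentation. The evaluability loss needs the ring to stop on Day 56 while the participant still has it, which nothing in the documents describes as a planned step. The minute figures are assumptions. The epoch wording is put right by the sentence before it and by Appendix A, to which 6.1.7.3 refers. The table in SAP 6.1.5 is introduced for early-termination and unscheduled visits.

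Much of this stands. The visit anchor is a permissible reading and a defensible choice, the evaluability loss is conditional, and the epoch point is a wording repair. The 6.1.5 remark changes nothing, because Protocol Table 3 gives the same 7-day allowance. What remains is that Section 10.4.2 and Section 5.5 name the fixed days outright, Section 7.1.1 equates them with the period before the visit, and the SAP uses other nights for late visits without saying so. Section 4.1 governs collection and does not alter the analysis window. On epochs, Appendix A's *and* wording can itself be read as the union of two sets, so the SAP has three wordings and no single clean rule.

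**Conclusion.** Both parts hold. For a Day 56 visit the two documents agree apart from the 7-or-8-day count. For later visits the overlap falls to no shared night at Day 63 (waking-day dating) or one (start-day dating). This is a flaw in how the primary variable is specified; it does not show that the result would be wrong.

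The number of participants affected and the direction of any bias cannot be derived from the documents. The effect on the mean is probably small: 2.3 to 5.7 minutes (one SD) against the 30-minute design effect, under the assumptions in step 4 and with all 47 visits late. The per-protocol set with both assessments may be smaller than 47, which would widen that range by √(47/n); fewer late visits would shrink it. Any participant lost under the SAP window would leave the primary per-protocol analysis but stay in the ITT analysis with LOCF (SAP 8.1.1), provided an earlier rolling average exists.

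The literal epoch rule would give impossible totals and would probably be noticed, but the text defining the primary variable should be right.

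**What to change.** In SAP 6.1.7.3, name one primary Week 8 window: exactly 7 nights, a stated rule for dating a night, and at least 4 valid nights. Either anchor can be defended. If it stays anchored on the visit, list it in Section 10 with the reason. Run the other window as a sensitivity analysis and report how many participants are evaluable under each.

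In 6.1.7.3 and Appendix A, use one epoch rule: the epoch ends after 6 pm on the previous day **and** starts before 9 am on the day. Confirm that an epoch crossing either limit is counted whole.

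The cost is SAP wording, one line in Section 10 and one extra table from ring data already collected. The drawback is that a few participants may be evaluable under only one of the two windows, so the two analyses may not cover exactly the same people.

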6.1.7.4. PROMIS 8a

The PROMIS 8a form is a validated instrument used to measure the severity of sleep-related impairment. A higher PROMIS score indicates more severe sleep impairment. The PROMIS score includes 8 items and uses a 1-5 severity scale and is filled out weekly. The questionnaires are required to be filled out in their entirety in order to save.

[figure not shown]
The PROMIS total score will be calculated as the sum of the 8 items and will range from 8 to 40.

[figure not shown]
The baseline PROMIS 8a score will be the last score on or before Visit 1, the Visit 2/Week 4 score will be the last score on or before V2 within 7 days, and the Visit 3/Week 8 score will be the last score on or before V3 within 7 days.

[figure not shown]

[figure not shown]

[figure not shown]
6.1.8. Data Adjustments/Handling/Conventions

All collected data will be presented in listings. Data not subject to analysis according to this plan will not appear in any tables or graphs but will be included only in the data listings.

All p values will be displayed in four decimals and rounded using standard scientific notation (eg, 0.XXXX). If a p value less than 0.0001 occurs, it will be shown in tables as < 0.0001.

Adverse events will be coded using the MedDRA version 27.1 thesaurus.

A treatment related AE is any AE with a relationship to the study drug of possibly related.

If partial start dates occur for AEs, prior medications, or concomitant medications, the convention for replacing missing dates for the purpose of statistical analysis is as follows:

- If the year is missing do not impute
- If only the day is missing and the month and year match the first dose date and the end date is on or after the first dose date, then the day assigned is equal to the first dose date; if the month and/or year do not match the first dose date or the end date is prior to the first dose date, then the day is assigned 01.
- If only the month is missing and the day and year match the first dose date and the end date is on or after the first dose date, then the month assigned is equal to the first dose date; if the day and/or year do match the first dose date or the end date is prior to the first dose date, then the month assigned is JAN.
- If both the month and day are missing and the year matches the first dose date and the end date is on or after the first dose date, then the date assigned is the first dose date; if the year does not match the first dose date or the end is prior to the first dose date, then the day/month is assigned 01JAN.

Partial end dates will not be imputed.

7. Study Patients/Subjects and Demographics

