6.1.7. Derived Variables

6.1.7.1. General

- Age: Age will be calculated as the integer difference in years between the subject's year of informed consent and the year of birth.
- Change from baseline: The value at the target time point minus the value at baseline.
- Prior and concomitant medications: All medications taken prior to Screening or in the time interval between Screening and Enrollment/Visit 1 will be considered prior medications, whether or not they were stopped before Enrollment/Visit 1. Any medications continuing or starting after Enrollment/Baseline Visit will be considered concomitant. If a medication starts before enrollment and continues after enrollment it will be considered both prior and concomitant.
- **Study Day:** For analysis purposes, Study Day is calculated relative to the date of first dose of study drug. For study days on or after treatment start, study date = date treatment start date + 1. For study days before treatment start, study day = date treatment start date.
- Treatment-emergent adverse event (TEAE): Defined as 1) AEs with onset at the time of or following the start of treatment with IP through Week 8 (EOT) or 2) AEs starting prior to the start of treatment but increasing in severity or relationship at the time of, or following, the start of treatment with IP through Week 8 (EOT).

[figure not shown]

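### SAP 6.1.8: the month-missing date rule contradicts itself, and restoring the dropped 'not' would still date most such on-treatment adverse events before first dose

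*SAP*

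**What the plan says.** SAP 6.1.8 has three rules for partial start dates of AEs and of prior or concomitant medications. Each has a matching branch and a fallback branch.

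- **Month missing, matching branch.** The condition on the start date is "If only the month is missing and the day and year match the first dose date". An end date no earlier than first dose is also required. The result is the first-dose month.
- **Month missing, fallback branch.** The condition is "if the day and/or year do match the first dose date or the end date is prior to the first dose date". The stated result for such a record is "then the month assigned is JAN".
- **Day missing, fallback condition:** "if the month and/or year do not match the first dose date". An end date before first dose also triggers it.
- **Day and month both missing, fallback condition:** "if the year does not match the first dose date". An end date before first dose also triggers it. The matching branch, which needs a matching year and an end date on or after first dose, assigns the first-dose date itself.

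The section closes its date conventions with "Partial end dates will not be imputed".

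SAP 9.1 applies these imputed dates to the AE analysis. SAP 6.1.7.1 counts an AE as treatment-emergent if it starts at or after the start of treatment through Week 8, or if it started earlier and then increased in severity or relationship on treatment. Protocol 10.4.5 limits the AE analysis to TEAEs, with all AEs listed.

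**The concern.** There are two separate faults.

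1. **Wording.** With 'do match' in the fallback branch, the month-missing rule cannot be programmed as printed. It gives two answers in one case and none in another.
2. **Substance.** The matching branch requires the start day to equal the first-dose day number. Few on-treatment starts do, so most go to January whatever the end date shows. A record with the day known is then treated less cautiously than one with day and month both unknown, which is set to the first-dose date when the year matches and the end date is on or after first dose.

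At stake is TEAE status. An on-treatment event dated to January drops out of the TEAE tables, so the error runs towards under-counting. If all 47 enrolled participants were treated, one participant is 1/47 = 2.1 percentage points in an incidence table.

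**Working it through.** The plan states no figure for this rule, so there is none to reproduce. The check traces the logic and then enumerates cases.

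**Step 1. Month missing, as printed, end date on or after first dose.**

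| Known parts against first dose | Matching branch | January branch |
|---|---|---|
| Day and year both match | applies | applies: conflict |
| Year matches, day does not | no | applies |
| Day matches, year does not | no | applies |
| Neither matches | no | no: gap |

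**Step 2. With 'not' restored.** The first row gives only the first-dose month and the other three give January. Conflict and gap disappear. The second row, a same-year start on a different day number, still goes to January.

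**Step 3. Enumeration.**

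- Inputs: 56 treatment days (Protocol, Table 2) and screening of at most 42 days (Protocol 8.1.2).
- Assumptions: first doses spread evenly over one 365-day year (2023 used), true onset on each of Study Days 1 to 56, month missing, end date known and on or after first dose.
- Pairs: 365 × 56 = 20,440, of which 18,900 have onset in the same calendar year as first dose and 1,540 in the next.

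| Result | Pairs | Share of 20,440 |
|---|---|---|
| Printed rule: both branches apply | 692 | 3.4% |
| Printed rule: no branch applies | 1,509 | 7.4% |
| Printed rule, matching branch given priority: dated before first dose | 17,371 | 85.0% |
| Printed rule, January given priority: dated before first dose | 18,004 | 88.1% |
| 'Not' restored: dated before first dose | 17,371 | 85.0% |
| 'Not' restored: dated more than 42 days before first dose | 15,110 | 73.9% |
| Day-missing rule: dated before first dose | 0 | 0% |
| Day-and-month-missing rule: dated before first dose | 0 | 0% |

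With 'not' restored, the 18,900 same-year pairs split into 692 set to first dose, 837 whose January date is still on or after first dose, and 17,371 dated before it: 692 + 837 + 17,371 = 18,900. The same-year share is 17,371 / 18,900 = 91.9%. None of the 1,540 next-year pairs is dated before first dose.

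**Step 4. One case.** First dose 10 June 2023, true onset 20 June 2023 (Study Day 11), month not recorded, end date after first dose. The year matches and the day does not, so the printed rule and the rule with 'not' restored both give 20 January 2023, Study Day −141. AEs are recorded only if they begin or worsen after consent (Protocol 8.4.1), and consent could not be earlier than 42 days before dosing, 29 April. A January onset is therefore impossible for an event that began after consent.

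**Step 5. Missing end dates.** In the day-missing and day-and-month-missing rules, a start whose known parts match first dose but which has no end date meets neither branch: one needs an end date on or after first dose, the other a mismatch or an earlier end date. The month-missing rule has the same gap once 'not' is restored. Where the known parts do not match, the fallback applies without an end date.

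**The case against.** The strongest reply is that this hardly matters. A start date with day and year known but month missing is unusual, the documents give no frequency for it, and SAP Section 4 requires a thorough data review before analysis. The 85.0% is conditional on that pattern and on evenly spread first doses, and the enumeration contains only true on-treatment onsets. All of this stands. It limits the practical weight, but it does not make the rule right.

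Four stronger readings are tempting and are not supported.

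- **That every safety table is affected.** Laboratory and vital-sign tables do not use TEAE status (SAP 9.2, 9.3). Deaths and serious AEs are listed (SAP 9.1.2), and the listing of all AEs flags those that are not treatment-emergent (SAP 9.1). Tabulation of TEAEs is affected, not data capture.
- **That every such event is misclassified.** In the enumeration 15.0% of on-treatment onsets are not dated before first dose, and an earlier event that worsens on treatment still counts under the second part of the TEAE definition.
- **That an end date after dosing proves on-treatment onset.** With first dose 10 June, start day 15 and end 20 July, onset could have been 15 May: 26 days before dosing, within the 42-day screening limit, and correctly not treatment-emergent unless it worsened.
- **That the dropped word causes the misclassification.** It causes the conflict and the gap. The January default does the rest and survives the correction.

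**Conclusion.** The month-missing rule is wrong as written, and a one-word correction is not sufficient. Among on-treatment AEs with only the month missing, about 85% would be dated before first dose (91.9% when onset is in the same calendar year) and would leave the TEAE tables unless they worsened on treatment. The two sibling rules pre-date none under the same conditions.

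The percentages rest on evenly spread first-dose dates, onset on Study Days 1 to 56, and a known end date on or after first dose. They describe how the rule behaves and are not a forecast of how many events will be lost. That number is unknown and probably small, so this is a minor correction, worth making because it is cheap and the error runs towards under-reporting.

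**What to change.** In SAP 6.1.8:

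1. Restore 'not' in the fallback branch of the month-missing rule.
2. For AEs with only the month missing, replace the January default. If the year matches first dose and the end date is on or after first dose, missing or ongoing, impute the earliest date on or after first dose that fits the known day and year and is not after a known end date. If no such date exists, or the year does not match, or the end date is before first dose, impute the earliest date consistent with the known parts.
3. In all three rules, treat a missing or ongoing end date as on or after first dose. Leave the day-missing rule otherwise unchanged.
4. Keep the earliest-date convention for prior and concomitant medications. Moving those starts forward could take a drug out of the prior-medication table.

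The end-date limit and the no-solution clause are both needed. With first dose 10 June, start day 05 and end 20 June, the next 5th is 5 July, after resolution; the clause returns 5 January, correctly before treatment. With first dose 10 December and start day 05 in the same year, no date on or after first dose exists.

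In the same 20,440 pairs, with the end date either missing or set to the onset day, this rule dates no onset before first dose and none after a known end date. The Step 4 case becomes 20 June 2023.

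The cost is a few lines of SAP text and programming, plus slight over-counting of TEAEs: the 15 May onset described above would be imputed to 15 June. If the tables are already programmed, state in the study report which rule was used and check the AE listing for starts with only the month missing.
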